This study aims to compare quality of recovery as well as peri-operative systemic opiates use and pain scores in patients undergoing laparoscopic or robotic hysterectomy when local anesthetic versus Quadratus Lumborum nerve block (QL-2) is added to the standard pain management.

Primary Outcome measure:

For the primary outcome, we plan to Compare the Quality of Recovery (QOR-40) validated questionnaire scores between different arms

a. At 24 hours

The Quality of Recovery-40 (QoR-40) questionnaire measures the quality of recovery from anesthesia through five dimensions: physical comfort, physical independence, emotional state, psychological support, and pain. The validity, reliability, ease of use, responsiveness, and cross-cultural adaptation of QoR-40 have been previously confirmed and this questionnaire has been used successfully in several clinical trials. (27). (Appendix 1). This questionnaire takes 6.3 min to complete and will be filled by the research assistant.

Secondary Outcome measures:

1. *Compare* pain score (rest and dynamic as coughing or moving from lying down to sitting up) between the interventions at several time points: Patients will be instructed to use the visual analog scale (NRS), 0 corresponding to no pain at all and 10 corresponding to worst imaginable pain) at different time points,
 - a. PACU immediately postoperatively
 - b. At the time of first opiate administration,
 - c. At the time of discharge (most patients are discharged the same day)
 - d. On day 1 (24+/-4 hours),
 - e. On day 14
 - f. At 6 weeks
2. To collect these pain scores, the EHR will be used to extract the VAS scores documented by the RN while the patient is in the PACU and until the patient is discharged from the hospital.
3. A telephone call will be done at 24 hours (+/-4 hours) by the research assistant blinded to the procedure and the patient will be seen by the physician in the office at the 2 and 6 weeks mark as per usual care.
4. Compare time to administration of first pain medication in the hospital.
5. Estimate PONV scores (Worst score) before discharge across different interventions. Scale: (none, mild, moderate severe).
6. Compare the time needed to administer the intervention QL Block.
7. Compare opiate use in the postoperative period measured in oral morphine equivalent (OME)
 - a. In the first 24 hours after the surgery (which is the duration of the block).
 - b. 2 weeks post-surgery.
 - c. 6 weeks post-surgery

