8. We will use the oral morphine conversion table to convert any opiate use to OME for each patient (26).
9. Assess possible complications with each intervention (expected to be low).

Study Population

- All female patients undergoing laparoscopic or robotic hysterectomy at MHH and will be recruited and consented for enrollment by the research team in the preoperative area.

Inclusion Criteria:

- English or Spanish speaking
- American Society of Anesthesiologists (ASA) physical status 1-3,
- Age greater than or equal to 18 years
- Planned laparoscopic or robotic hysterectomy

Exclusion Criteria:

- History of chronic pain requiring preoperative opioids, Known alcoholism disorder
- Congenital coagulopathy,
- Localized soft tissue infection,
- Use of anticoagulants,
- Dementia, inability or refusal to provide consent for the surgery
- Morbid obesity (BMI > 50), due to expected technical difficulty to achieve the block.
- Usual pain management will continue regardless of which arm of the study patients are in and measurements of pain scores, narcotic usage and abdominal numbness will be assessed in the post-operative period.

Study Design and Procedures

The study will be reported according to the CONSORT (Consolidated Standards of Reporting Trials) guidelines (28).

All medications and procedures used in this study (0.25% bupivacaine, dexamethasone, acetaminophen, ibuprofen, QL blocks) are FDA approved and have been determined to be usual care in the coverage analysis.

1- Recruitment and consents:

Patients undergoing laparoscopic or robotic hysterectomy at MHH will be recruited and consented for enrollment and block randomized to one of 2 arms: Local anesthesia and QL block. The regional anesthesia nurse would consent the patients.

Spanish consents are available for Spanish speaking patients.

Patients will not be told if they will be receiving the drug or the control.

Blinding is done by the nurse anesthetist preparing the medication, to assure anesthesiologist and research personnel are blinded to the drug used since each patient will receive the two modalities, with only one containing the active drug.

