All patients will receive the same post-operative pain medication regimen (this regimen is obtained via consensus from anesthesiologists and surgeons performing minimally invasive hysterectomy).

We will give the patients a Gabapentin, Tramadol prescription (50 mg X15 tablets as the only opiate) in addition to the Ibuprofen and Tylenol (See the ERAS protocol for details).

- Tylenol total 30 tab
- Ibuprofen 600 mg q6hr total 30 tab
- Gabapentin 300 mg total 20 tab
- Tramadol 50 mg total 15 tab

5- Comparison:

The following variables will be recorded to compare the different interventions in the following timeline:

- In PACU: (Registered nurse, performs usual care) data is collected retrospectively by research staff
 - Collect pain score rest and dynamic using the Visual analog scale (VAS)
 - Immediately upon arrival
 - At the time of first opiate use
 - Worst pain score
 - At time of discharge
 - Postoperative nausea and vomiting (PONV) score (worst and at the time of discharge)
 - Time elapsed to first opiate use (in minutes)
 - Cumulative opiate use in OME in PACU
 - patient satisfaction will be measured on a Likert scale (5 points)
 - The incidence of postoperative adverse events such as nausea, vomiting, dizziness, headache, urinary retention, local anesthesia-induced side effects (paresthesia, hearing disturbance, visual disturbance, and dysarthria)
- At 24 hours (+/- 4 hours) telephone call by research assistant blinded to procedure
 - Filled Tramadol (Yes/no)
 - Cumulative opiate use in OME if any (How many Tramadol pills used).
 - QOR-40 (6.3 min validated questionnaire)
 - Dynamic pain score on VAS
 - Patient satisfaction will be measured on a Likert scale (5 points)
- Day 14: (clinic visit, usual care)
 - Filled Tramadol (Yes/no)
 - Cumulative opiate use in OME if any. (Via number of Tramadol pills left)
 - Dynamic pain score on VAS
 - Clinic visit on day 14 (per usual care)
 - Cumulative opiate use in OME if any (Check number of pills of Tramadol left. Versus need for refills).
 - Dynamic pain score on (VAS).
- 6 weeks clinic visit (per usual care)
 - Complications

- Cumulative OME use if any
- Refill on pain meds, yes/no and which medications.

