During the telephone encounters or the clinical visits, patients will be asked if they filled their prescription for Tramadol/narcotic and how many pills they have left). If the patient is not seen at the 2 weeks mark for any reason, a telephone call will be done to collect that information by the surgeon.

6- Expected duration of study and subject participation.

We currently perform at the minimum 5 hysterectomies per week and Memorial Hermann Hospital (Laparoscopic and Robotic) and expect to randomize half of the patients, to complete the study within up to 2 years after IRB approval.

Sample Size and Power

- Based on previous studies, the mean standard deviation of QOR-40 after gynecologic laparoscopy are 150-170 and 10-15, respectively.
- A clinically significant difference would be 10-15.
- A sample size of 31 patients per group is needed to detect the difference of 20 points in the global QOR-40 score, a SD 25, with a Type 1 error of 5% and a power of 90%.
- 76 patients will be included to allow for a dropout rate of approximately 18%. Lost to follow up is expected to be low.

For pain scores in the VAS: Meaningful clinical difference in VAS scores is 30%

Analysis Plan/Statistics

- For baseline patient characteristics, continuous variables will be reported as medians with 25th and 75th percentiles (interquartile range [IQR]), and categorical variables as counts and percentages.
- To compare across groups, Kruskal-Wallis tests will be performed for continuous variables and Chi-square tests for categorical variables.
- CONSORT diagram will be performed
- Intention to treat analysis will be performed
- All unadjusted outcomes will be reported descriptively (mean SD/ median IQR)
- For all outcomes, we will conduct intent-to-treat Bayesian analysis to calculate probabilities of intervention benefits and harms. We will use neutral priors and exclude large treatment effects. We will report posterior medians of group differences, their corresponding 95% credible intervals, and probability of treatment benefit.

Primary outcome as QOR will be analyzed with a negative binomial regression model to account for expected skewness. The model will include group (local, QL), and type of surgery as covariates. We will account for surgery type (Robotic versus laparoscopic hysterectomy) simply because of the difference in port placement and port size between both approaches.

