- We will report risk ratios and 95% confidence intervals comparing local to QL block. We will assess the normality of the data and robustness of the conclusion using the appropriate tests.
- As the pain scores are repeated over time, a linear mixed model analysis (patient as random intercept, patient-time as random slope, unstructured covariance) will be undertaken to identify any treatment differences across time.
- Arrival to PACU is defined as time 0.

All opioid or pain medications are registered in the subject's electronic file and are tallied to form the total postoperative opioid consumption.

FUNDINGS:

There is no funding for the study, this is PI initiated.

The cost will be that of the catheters for the blocks which will be donated to the anesthesiologist and no charges are incurred to the patient or the hospital. The anesthesia research team will waive billing for the QL procedure for the study patients. Local anesthesia is bundled with the surgery and does not constitute a separate charge. Local anesthesia is bundled with the surgery and does not constitute a separate charge. The placebo is just 20 mls of saline solution.

OVERSIGHT RESPONSIBILITIES

Oversight of the trial is provided by the Principal Investigator (PI), [name] and Co-investigators Drs [name] and [name] *who will be actively involved in the conduct of the study.*

MONITORING PROCEDURES

[name] assures that informed consent is obtained prior to performing any research procedures, that all subjects meet eligibility criteria, and that the study is conducted according to the IRB-approved research plan.

Study data are accessible at all times for the PI and co-investigators to review. [name] and [name] will review study conduct: accrual, drop-outs, protocol deviations on a quarterly basis. The PI, CO-PIs will review AEs individually real-time and in aggregate on a quarterly basis. They will also review serious adverse events (SAEs), including anesthetic allergy, local anesthetic toxicity, as well risk of infection in real-time. The PI ensures all protocol deviations, AEs, and SAEs are reported to the IRB according to the applicable regulatory requirements.

COLLECTION AND REPORTING OF SAEs AND AEs

For this study, the following standard AE definitions are used:

Adverse event: Any unfavorable and unintended sign (including an abnormal laboratory finding), symptom or disease temporally associated with the use of a

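### Chi-square is the only test named for categorical variables; if applied to PONV and satisfaction it ignores their ordering and loses roughly 10 to 25 points of power

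*Combined protocol and SAP*

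**What the plan says.** The Analysis Plan/Statistics section opens with a bullet on baseline description: "For baseline patient characteristics, continuous variables will be reported as medians with 25th and 75th percentiles". The next bullet, on comparison across groups, states: "Kruskal-Wallis tests will be performed for continuous variables and Chi-square tests for categorical variables". It does not say whether it covers baseline variables, outcomes or both.

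Later in the same section, outcomes receive a further analysis: "For all outcomes, we will conduct intent-to-treat Bayesian analysis to calculate probabilities of intervention benefits and harms". Two more sentences could bear on the point: "We will report risk ratios and 95% confidence intervals comparing local to QL block", which names no outcomes, and "We will assess the normality of the data and robustness of the conclusion using the appropriate tests", which names no test. No trend test, rank test for ordered categories or ordinal regression appears anywhere.

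Two of the variables compared between arms are ordered categories:

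- Worst PONV before discharge is item 5 of the secondary outcome measures, with four levels: "Scale: (none, mild, moderate severe". The Comparison section also records PONV at discharge.
- In the Comparison section, "patient satisfaction will be measured on a Likert scale (5 points", once in PACU and again at the 24-hour call. Satisfaction is not in the numbered list of secondary outcomes.

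**The concern.** With two arms, Pearson chi-square on an ordered scale asks only whether the two sets of proportions differ in any way. Swapping the mild and severe columns would leave its p-value unchanged. The clinical question is whether one arm is shifted towards less nausea or higher satisfaction. A method that uses the order puts its power on that one direction, whereas chi-square spreads it over every possible pattern of difference.

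At stake is the chance of detecting a real shift on these two scales. Chi-square also gives no effect estimate, so it would not summarise the size or direction of a shift.

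**Working it through.** **Inputs from the plan.** There are two arms. The Sample Size and Power section gives 31 per group and 76 in total. PONV has 4 levels and satisfaction 5. The plan gives no level distribution, target effect or power for either scale, so those inputs below are assumptions.

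**The plan's own figures.** The 31 per group was set for QoR-40 (difference 20, SD 25, 5% error taken as two-sided, 90% power). The normal formula gives 2 × (1.960 + 1.282)² × 25² / 20² = 2 × 10.51 × 1.5625 = 32.8, so 33. This is close to 31, where power is 0.883. The dropout step reproduces: 62 / (1 − 0.18) = 75.6, so 76, or 38 per arm. Neither figure was derived for a categorical outcome. They serve here only as the range of patients per arm.

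**Degrees of freedom.** Chi-square uses (2 − 1)(4 − 1) = 3 for PONV and (2 − 1)(5 − 1) = 4 for satisfaction. A rank test or proportional-odds comparison uses 1.

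**Assumed alternatives.** One arm has cumulative proportions c. In the other arm the cumulative odds c / (1 − c) are multiplied by a common odds ratio (OR). For PONV at 50/25/15/10% and OR 3, the cumulative odds 1, 3 and 9 become 3, 9 and 27. The cumulative proportions are then 0.750, 0.900 and 0.964, which gives 75/15/6.4/3.6%.

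**Simulation.** There were 10,000 trials per setting at the 5% level, comparing uncorrected Pearson chi-square with the tie-corrected Wilcoxon test. Power is chi-square / rank test, with the loss in points in brackets.

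| Assumed scale in one arm | Per arm | OR 2 | OR 3 | OR 4 |
|---|---|---|---|---|
| PONV 50/25/15/10% | 31 | 0.167 / 0.276 (11) | 0.373 / 0.562 (19) | 0.535 / 0.729 (19) |
| PONV 50/25/15/10% | 38 | 0.204 / 0.324 (12) | 0.463 / 0.642 (18) | 0.639 / 0.813 (17) |
| PONV 70/15/10/5% | 31 | 0.110 / 0.206 (10) | 0.225 / 0.398 (17) | 0.328 / 0.543 (22) |
| PONV 70/15/10/5% | 38 | 0.134 / 0.249 (12) | 0.271 / 0.473 (20) | 0.398 / 0.623 (22) |
| Satisfaction 3/5/12/35/45% | 31 | 0.156 / 0.303 (15) | 0.401 / 0.646 (25) | 0.609 / 0.833 (22) |
| Satisfaction 3/5/12/35/45% | 38 | 0.197 / 0.373 (18) | 0.491 / 0.731 (24) | 0.724 / 0.905 (18) |

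With no true difference (OR 1), rejection rates were 0.032 to 0.049 for chi-square and 0.046 to 0.053 for the rank test. The rank test's advantage is therefore not bought with excess false positives.

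**Second set of distributions.** A separate simulation used 6,000 trials per setting and 31 per arm. With PONV at 40/30/20/10%, power was 41% against 59% at OR 3 and 30% against 47% at OR 2.5. With satisfaction at 30/35/20/10/5%, it was 40% against 63% and 26% against 48%. The losses of 17 to 23 points lie inside the range in the table.

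**The case against.** **Scope.** The chi-square bullet directly follows the baseline bullet and uses the same continuous/categorical split, and outcomes are introduced only afterwards. A baseline-only reading is natural and may be what was meant. This stands as a limit on the point: the power loss arises only if the sentence is applied to outcomes. On the narrow reading, however, the plan names no test for PONV or satisfaction at all, so the same addition is needed.

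**The rank test is already there.** With two groups, Kruskal-Wallis is the Wilcoxon test. An analyst who filed these scales under continuous variables would lose nothing. But the plan does not assign ordered scales to either class, and that choice should not be left until the data are seen.

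**Other analyses.** A reader might infer that chi-square is the only analysis planned for these outcomes. The documents do not support that, because the Bayesian analysis is stated for all outcomes, with credible intervals and a probability of benefit. What remains is that no likelihood is given for an ordered scale, and a posterior median group difference has no defined meaning on four labelled levels until one is chosen.

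**Assumed effects.** The distributions and odds ratios are not the plan's. Even the rank test reaches only 0.21 to 0.37 power at OR 2, so the trial is not sized for these scales under either method. That is correct. The argument is about the relative loss, which appeared in every alternative tried.

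**Conclusion.** The point holds as a conditional one. Chi-square is the only test named for categorical variables. If it is used for PONV and satisfaction, it discards their ordering and loses about 10 to 25 percentage points of power. That size rests on assumed distributions, proportional-odds shifts with odds ratios of 2 to 4, and 31 to 38 patients per arm. Only PONV and satisfaction are affected. The QoR-40 primary analysis and the mixed model for pain scores are not.

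Two wider inferences are tempting, and the documents support neither:

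- **That chi-square is wrong for all the categorical outcomes.** Whether tramadol was filled and whether any opiate was used are yes/no variables. They are neither ordered nor described as rare, and chi-square can suit them.
- **That chi-square would produce false harm signals for complications, so that Fisher's test must replace it.** The plan does say "Assess possible complications with each intervention (expected to be low". A split of 4/38 against 0/38 gives p = 0.040, but only without a continuity correction, and the plan does not specify either form. With the correction p = 0.123, close to Fisher's 0.115. Even uncorrected, the exact false-positive rate at 38 per arm is 0.006 at a 2% event rate, 0.041 at 5% and about 0.058 at its highest. Fisher's rate is 0.003 at a 5% event rate and 0.015 at 10%. It is far more conservative, so moving to it is a debatable trade-off and not a correction.

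**What to change.** Limit the chi-square sentence to baseline and unordered categorical variables, and add text such as:

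> PONV and satisfaction are ordered outcomes. At each time point they will be compared between arms with a proportional-odds model including group and surgery type, reporting the common odds ratio and its 95% interval. A Wilcoxon test will be given as a check. The Bayesian analysis of these outcomes will use the same ordinal likelihood.

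Including surgery type matches the adjustment already planned for QoR-40. The common odds ratio also gives the Bayesian analysis a defined group difference to summarise.

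The cost is a few sentences in the analysis plan, with no new data or patients. The downside is reliance on proportional odds, so the level counts by arm should be tabulated to let readers judge it. The change should be made before allocation is unblinded.

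### The plan states the relevant QoR-40 effect in points but promises no adjusted points difference with a 95% CI; its negative binomial model yields a ratio and cannot fit the smaller SDs it expects

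*Combined protocol and SAP*

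**What the plan says.** Under Sample Size and Power, the scale is points. The plan states "A clinically significant difference would be 10-15" (unit implied), and 31 patients per group are "needed to detect the difference of 20 points in the global QOR-40 score, a SD 25". The same section expects QoR-40 means of 150-170 and SDs of 10-15 after gynecologic laparoscopy.

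Under Analysis Plan/Statistics, several outputs could bear on the 24-hour QoR-40:

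- **Primary model:** "Primary outcome as QOR will be analyzed with a negative binomial regression model to account for expected skewness". Its covariates are group and type of surgery (robotic or laparoscopic).
- **Next bullet:** "We will report risk ratios and 95% confidence intervals comparing local to QL block". It names no outcome. It is followed by "We will assess the normality of the data and robustness of the conclusion using the appropriate tests".
- **Descriptive:** "All unadjusted outcomes will be reported descriptively (mean SD/ median IQR".
- **Bayesian, for all outcomes:** "We will report posterior medians of group differences, their corresponding 95% credible intervals, and probability of treatment benefit". Scale, likelihood and covariates are not given.
- **Rank test:** "To compare across groups, Kruskal-Wallis tests will be performed for continuous variables". It directly follows the baseline bullet, and its scope is unclear.

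No sentence says which result carries the conclusion.

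**The concern.** A negative binomial model with its usual log link estimates the ratio of mean scores. If the risk-ratio bullet describes that output, the label is wrong, because a questionnaire score has no risk. If the bullet is meant for the plan's yes/no outcomes (opiate use, tramadol filled), the primary model has no stated effect measure. On either reading, the result the clinical reader needs is not promised: how many QoR-40 points QL adds, adjusted for surgery type, and with what uncertainty.

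The choice of model raises a second matter. It was chosen to handle skewness, but it also fixes a lower limit on the variance, and that limit falls inside the SD range the plan itself expects.

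**Working it through.** **Inputs.** From Sample Size and Power: means 150-170, expected SD 10-15, design SD 25, relevant difference 10-15, design difference 20, 31 per group. Assumed: 1:1 allocation, two-sided 5% tests, and higher scores meaning better recovery.

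**1. The plan's own figure.** n per group = 2 × [25 × (1.960 + 1.282) / 20]² = 32.8, so 33 against 31 stated; power at 31 is 88.3%. The total follows from 62 / (1 − 0.18) = 75.6, so 76. These are close enough to confirm that the design was built on a difference in means, in points.

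**2. Points expressed as ratios.** QL/local = (m + d)/m; local/QL = m/(m + d), where m is the local mean and d the QL benefit.

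| d | QL/local, m = 150 | QL/local, m = 170 | local/QL, m = 150 | local/QL, m = 170 |
|---|---|---|---|---|
| 10 | 1.067 | 1.059 | 0.938 | 0.944 |
| 15 | 1.100 | 1.088 | 0.909 | 0.919 |
| 20 | 1.133 | 1.118 | 0.882 | 0.895 |

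Only QL/local ratios of 1.059-1.067 change side of 10 points between the two means. Conversion is therefore minor once the means are known; the missing item is the adjusted interval.

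**3. Width of that interval.** Half-width = t(0.975, 59 df) × SD × √(2/31), with t = 2.001: 5.1 points at SD 10, 7.6 at SD 15 and 12.7 at SD 25. These are of the same order as the 10-15 point range.

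**4. A conditional example.** Suppose the local mean is 160, the SD 15 and QL is 12 points better.

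- In points: 12 ± 7.6, that is 12 (4.4 to 19.6).
- As a ratio: SE of the log ratio = √{[(15/160)² + (15/172)²]/31} = 0.0230, so QL/local = 1.075 (1.027 to 1.126).
- Inverted: local/QL = 0.930 (0.888 to 0.974).

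The published line would be a risk ratio of 0.93 only if the bullet refers to QoR-40 and its local-to-QL direction is literal.

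**5. Variance floor.** Negative binomial variance = mean + α × mean², with α ≥ 0, so the SD cannot be below √mean. If the true SD is 10, the model-based SE is too large by the factor √mean / 10. A nominal 5% test then rejects with probability 2 × [1 − Φ(1.96 × factor)].

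| Mean | Smallest SD the model allows | SE factor at SD 10 | Actual size of 5% test |
|---|---|---|---|
| 150 | 12.2 | 1.22 | 1.6% |
| 160 | 12.6 | 1.26 | 1.3% |
| 170 | 13.0 | 1.30 | 1.1% |

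**6. Simulation.** 2,000 replicates, 31 per group, arm plus surgery type, and a rounded scaled-beta score on an assumed 40-200 range that is not in the documents. Results are in the order mean 150/160/170.

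- SD 10, no effect, rejection: model-based 1.8/1.0/1.0%; points difference from the same model with robust SE 5.1/4.9/4.7%.
- SD 10, 10 points, power: 93.0/91.7/90.5% against 96.8/97.0/96.5%. CI half-width: 6.25/6.45/6.65 against 5.11/5.11/5.10 points.
- SD 13, 10 points, power: 84.8/83.5/81.5% against 84.6/83.6/82.5%.
- SD 25, 20 points, power: model-based 86.9/86.9/83.2%; robust points difference 86.0/86.1/82.4%; linear HC2 85.9/86.3/82.5%; linear HC3 84.8/85.1/81.5%.

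The last figure in each SD 25 set is distorted: with a QL mean of 190, about 63% of simulated QL scores sit at the 200 ceiling. The cost of changing should be read from means 150 and 160.

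**The case against.** The best defence is that little would be lost in practice. Descriptive summaries are promised, and a Bayesian group difference in a score is most plainly in points. With means and SDs by arm, a reader can form a crude interval. Crude and adjusted results should be close: if half the cases are robotic, chance imbalance has SD √(2 × 0.25/31) = 0.127, so an assumed surgery-type effect of 5-10 points moves the crude difference by about 0.6-1.3 points. All of this stands and limits the harm. It does not close the gap, because the expected skewness could lead to medians being shown and because the Bayesian scale and covariates are unstated.

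Four stronger readings are tempting but not supported:

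- **That the trial will certainly report a risk ratio below 1 for a QL benefit.** The bullet names no outcome, and the model description lists local first, which fits local as the reference and a benefit above 1.
- **That a result fails unless its interval excludes 10 points.** The 10-15 range appears only under sample size; the plan sets no such rule.
- **That any result could be picked as the conclusion.** The negative binomial model is the only one tied by name to the primary outcome and is fairly clearly the intended lead. What is missing is a sentence placing the Bayesian result below it or beside it.
- **That the primary test is invalid.** The null hypothesis is the same on both scales, and the variance floor makes the test conservative. It disappears with robust standard errors, and the plan does not say which standard errors it will use.

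**Conclusion.** The point holds and should be fixed before analysis. The plan sets relevance and size in points but promises no surgery-type-adjusted points difference with a 95% CI, and on the natural reading it attaches the wrong effect label to a score. The consequence is mainly for interpretation.

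The loss of precision is real but confined to SDs near 10 with model-based standard errors: SEs 22-30% too large, an actual test size of about 1-2%, and 4-6 percentage points of power for a 10-point effect in the simulation. The floor calculation needs only the plan's means and SDs; the power figures also rest on the assumed score range and shape. Confidence is medium, because the scope of the risk-ratio bullet and the scale of the Bayesian output have to be inferred.

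**What to change.** Amend Analysis Plan/Statistics as follows:

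- **Primary estimate:** the QL-minus-local mean difference in 24-hour QoR-40 points, adjusted for surgery type, with a 95% CI from robust standard errors, shown beside the 10-15 point range. Name one source: a linear model, or the marginal difference from the negative binomial model, which may be kept.
- **Ratio, if also reported:** call it a ratio of means and state its direction. Keep the term risk ratio for binary outcomes.
- **Ranking:** state that this analysis leads and that the Bayesian analysis, on the points scale with the same covariates, is supportive.
- **Descriptive:** commit to QoR-40 means and SDs by arm, with medians in addition if wanted.
- **Robustness:** name the sensitivity analysis, for example a rank-based test or a bootstrap interval, and say whether Kruskal-Wallis covers QoR-40.

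The cost is a few lines of text, with no new data or patients. Simulated power at the design SD falls by about 1 percentage point with the robust marginal difference or linear HC2, and by about 2 with linear HC3.

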Assessment of safety: Safety of the procedure will be ensured by following ASA guidelines for regional anesthesia, as well as using ultrasound for placement of the nerve blockade as is standard of care. We will also ensure that post-operative medications are not prescribed to patients who may have an allergy to one of the medications, as well as adjusting the doses prescribed to patients who may have renal or hepatic dysfunction. The study will not incur more than minimal risk for the intervention and the placebo group.

Ethics

- IRB approval will be sought for this study.
- Patients will undergo standard consent for regional anesthesia and for participation in this study.
- The study was conducted in accordance with the Consolidated Standards of Reporting Trials (CONSORT) statement, the Helsinki Declaration, and monitored by the Good Clinical Practice Unit
- Will register the trial once the IRB is approved.

Data handling and record keeping

- Narcotic consumption, pain score patient data will be maintained in a secure file by the PI using Redcap to protect patient data.
- All nurses pre-operatively and post-operatively will be educated regarding the study and appropriate documentation of pain scores and medication requirements.

Publication Plan

- Plan to publish in the JMIG
- Results are not returned to subjects

Characteristic	N1	N2
Age		
Race		
Height		
Abdominal circumference		
Weight		
BMI		
Smoking		
Diabetes status		
Parity		
Hospital system		
Planned procedure		
Actual procedure		
Number of trocars used		
Largest trocar size (if single site used size of fascia incision)		
Largest trocar location		
Uterine size in grams		
Duration of surgery from cut to close		
Total anesthesia time		
Intraoperative complications		
Length of Hospital stay		

Incidence of adverse events	N1	N2
Nausea		
Vomiting		
Dizziness		
Headache		
Urinary retention		
Needle-insertion-site pain		
Hematoma		

Outcomes	N1	N2
Opiate use: yes/no		
Total number of Tramadol pills used, or other medications if any		
QOR-40 (6.3 min validated questionnaire)		
At 24 hours (+/- 4 hours): tel call by research nurse		
Cumulative Opiate use in (OME)		

OME in PACU		
OME At 24 hours (20-28 hours): tel call by research nurse		
OME at Day 14, Clinic visit		
OME at 6 weeks clinic visit (per usual care)		
Pain scores at rest		
PACU arrival		
PACU At the time of first opiate use		
PACU Worst pain score		
PACU At time of discharge		
At 36 hours (28-44 hours): tel call by research nurse		

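### Post-discharge pain scores follow three different schedules, and the 36-hour rows in the results table match no planned contact

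*Combined protocol and SAP*

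**What the plan says.** **Secondary Outcome measures.** Item 1 compares "pain score (rest and dynamic as coughing or moving from lying down to sitting up) between the interventions at several time points". After discharge these are "On day 1 (24+/-4 hours"), day 14 and 6 weeks. Item 3 gives the route: "A telephone call will be done at 24 hours (+/-4 hours) by the research assistant blinded to the procedure". For day 14 and 6 weeks it relies on the routine office visits with the physician.

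**5- Comparison.** This section sets out what will be recorded, contact by contact. In PACU it lists rest and dynamic pain. For the contact "At 24 hours (+/- 4 hours) telephone call by research assistant blinded to procedure", the only pain item is "Dynamic pain score on VAS". Day 14 also has dynamic pain only (entered twice). The 6-week list has complications, cumulative opiate use and "Refill on pain meds, yes/no and which medications", with no pain score.

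**Outcomes table at the end of the protocol.** Rest and dynamic pain each have four PACU rows, then "At 36 hours (28-44 hours): tel call by research nurse", day 14 and 6 weeks. Neither has a 24-hour row. The same table places QoR-40 at 24 hours (±4) and opiate use at 24 hours (20-28).

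**Analysis Plan/Statistics.** A linear mixed model is fitted to the repeated pain scores, with PACU arrival as time 0. The model's time points are not named.

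**The concern.** A pain score that is not asked for at the time cannot be reconstructed later. The Comparison list is the most operational of the three, and a data form would naturally be built from it. A form built that way would record no rest pain after discharge and no pain of either type at 6 weeks. The mixed model would then have only in-hospital scores for rest pain.

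The table raises a separate problem. The main objective in General Information (PICO) refers to pain at 24 hours, yet the table has no row for it and offers a 36-hour row that no contact feeds. Leaving 24 versus 36 hours unresolved also leaves the early reporting time open to be settled after data have been seen.

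The scope is limited to this secondary outcome. QoR-40 is placed at 24 hours consistently.

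**Working it through.** The plan states no figure on this point to reproduce. The check is a count of scores by pain type and time.

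**Step 1: scores promised.** Secondary Outcome measures: 2 pain types × 3 post-discharge times = 6 per patient.

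**Step 2: the three places side by side.**

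| Score | Secondary Outcome measures | 5- Comparison | Outcomes table |
|---|---|---|---|
| Rest, 24 h | yes | no | no |
| Dynamic, 24 h | yes | yes | no |
| Rest, day 14 | yes | no | yes |
| Dynamic, day 14 | yes | yes | yes |
| Rest, 6 weeks | yes | no | yes |
| Dynamic, 6 weeks | yes | no | yes |
| Rest, 36 h | no | no | yes |
| Dynamic, 36 h | no | no | yes |

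Of the six promised scores, the Comparison list has 2 (rest 0 of 3, dynamic 2 of 3). The table has 4 and adds two at 36 hours. Only dynamic pain at day 14 appears in all three places.

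**Step 3: could the 36-hour row be the 24-hour call?** The call window is 24 ± 4 = 20 to 28 hours. The row's window is 28 to 44 hours. They touch only at hour 28, so the overlap has zero width.

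**Step 4: scores not recorded if the Comparison list alone is followed.** Missing per patient: 6 − 2 = 4.

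- All 76 patients: 4 × 76 = 304 of 6 × 76 = 456.
- At the sample-size target of 2 × 31 = 62: 4 × 62 = 248 of 6 × 62 = 372.

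Both are two thirds of the promised post-discharge scores.

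**Step 5: table rows that could be filled.** Pain rows: 7 rest + 7 dynamic = 14. The Comparison list fills 4 PACU times × 2 types = 8, plus dynamic pain at day 14, giving 9. Five stay empty: rest and dynamic at 36 hours, rest at day 14, and rest and dynamic at 6 weeks. The 24-hour dynamic score that is collected has no row.

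**Step 6: is there another route?** The paragraph just before section 6 adds a telephone call for patients who miss the 2-week visit, but describes it as collecting prescription and pill-count information. It does not mention pain and sets up no 36-hour contact. The Background speculates about opiate use over 24-36 hours, which schedules nothing.

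**The case against.** The strongest reply has four parts.

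- **The conflict is narrower than three lists suggest.** The table agrees with Secondary Outcome measures on all four scores at day 14 and 6 weeks; its disagreement is confined to the early time point. This is correct, and it points to the Comparison list as the one that is short.
- **The loss is conditional.** The data form is not in the documents, so nobody can say that staff will follow the Comparison list alone. That stands: 304 is what that list implies as written, not a forecast. Likewise, 62 is a sample-size target, not a count of patients evaluable for pain. Of the 304, 3 × 76 = 228 fall at day 14 or 6 weeks, well beyond the 24 hours given as the block's duration; 76 are rest scores at 24 hours.
- **Pain at 24 hours is not wholly lost, and the table is an editable shell.** Dynamic pain is listed at the 24-hour call, and QoR-40 has a pain dimension. The 36-hour label may simply be stale. These points soften the table problem, but the QoR-40 dimension is not the promised 0-10 rest score, and correcting a label later does not recover scores that were never asked for.
- **The plan does not say that rest and dynamic pain are modelled separately.** True. But if they were pooled, every post-discharge score from the Comparison list would be dynamic, so change over time would be mixed with change in the type of pain measured.

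Text extraction is not a good explanation either. The 6-week list may cross a page break, but the rest items missing at 24 hours and day 14 do not, and the 36-hour row appears intact twice.

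**Conclusion.** The concern holds. The Comparison list contains 2 of the 6 promised post-discharge pain scores, and the table's 36-hour rows correspond to no planned contact. The loss of 304 of 456 scores, and the five empty table rows, rest on one assumption: that data collection follows the Comparison list alone. If staff instead follow Secondary Outcome measures, no promised score is lost, but the table still has no place for 24-hour pain. The point should be corrected before recruitment. It concerns a secondary outcome and its mixed model, and leaves the primary analysis untouched.

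**What to change.** Use one schedule in all three places.

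1. In 5- Comparison, list rest and dynamic 0-10 scores at the 24±4-hour call, the day-14 visit and the 6-week visit.
2. Add the same two questions to the call already planned for a missed 2-week visit. State what is done when the 6-week visit is missed, since no fallback is described.
3. Relabel both 36-hour pain rows as 24 hours (20-28 hours), matching the opiate row.
4. In Analysis Plan/Statistics, name the time points in the mixed model, state whether rest and dynamic pain are modelled separately, and confirm that the 24 hours run from PACU arrival, already defined as time 0.
5. If a 36-hour score is really intended, add it as a separate planned contact in Secondary Outcome measures and 5- Comparison, not in place of 24 hours.

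Cost: four extra questions per patient (one at 24 hours, one at day 14, two at 6 weeks), all at existing contacts, plus edits to the list, the table shell and the model description. A real 36-hour score would add one contact per patient.
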